14.5. Safety Analyses

Safety will be evaluated based on the incidence of TEAEs, laboratory test results, vital signs, ECG findings, C-SSRS results, abnormal movement rating scales results, as well as concomitant medications. Reported AE terms will be coded using the MedDRA (Medical Dictionary for Regulatory Activities) preferred terms and system organ classes.

The incidence of TEAEs will be summarized for each study period, treatment group, and overall by severity and by relationship to study drug. The summary tables will include the number and percent of subjects with TEAEs overall, by system organ class, and by preferred terms within each system organ class. Additional AE summary tables will be defined in the SAP.

Laboratory tests will be summarized by visit for the absolute value itself and for change from baseline by study period. Tables showing the shift from baseline will also be presented.

Potentially clinically significant (PCS) values for each relevant parameter will be defined in the SAP.

QT, QTcB, and QTcF intervals will be calculated at each ECG assessment. Interval data will be summarized by study period and treatment group at each time point for the absolute value and for changes from baseline. In addition, the number and percentages of subjects with post-baseline results QTcB and QTcF values >450, 480, or 500 milliseconds and an increase from baseline of >30 or 60 milliseconds from baseline will be summarized. Other ECG variables that are collected will be summarized as well.

C-SSRS will be summarized by number and percent of subjects with any abnormal findings at post-baseline visits by study period and treatment group. AIMS, BARS, and SAS will be summarized by study period and treatment group for the absolute value and for changes from baseline at each visit.

Concomitant medications will be coded using World Health Organization Drug Dictionary Anatomical Therapeutic Chemical (WHO-ATC) class. The number and percentage of subjects using concomitant medications will be summarized by study period and treatment group.

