1.2. Summary of the Study Design

This is a Phase 2, multicenter, randomized, double-blind, placebo-controlled study designed to evaluate the efficacy, safety, and tolerability of ALKS 3831 in schizophrenia with AUD.

ALKS 3831 is a combination of olanzapine, an approved antipsychotic treatment for schizophrenia, and samidorphan, a new molecular entity.

Potential subjects for this study are adults with a diagnosis of schizophrenia (based on the Diagnostic and Statistical Manual of Mental Disorders 4th edition, text revision [DSM-IV-TR]) and AUD (based on DSM 5th edition [DSM-5]). Subjects must have recently (within the last 6 months) experienced an exacerbation of disease symptoms (eg, hospitalization) but cannot exceed a pre-defined level of symptom severity at the time of screening (as measured by the Positive and Negative Syndrome Scale [PANSS] and Clinical Global Impression-Severity [CGI-S]).

[figure not shown]
All study visits will be outpatient visits. After informed consent and screening, subjects will begin a 4-week open-label olanzapine dosing period followed by a 2-week open-label ALKS 3831 period (see [Figure 1](#)). Once-daily, open-label olanzapine dosing will begin at Visit 2 with the dose level determined by the principal investigator (PI). Once daily open-label ALKS 3831 dosing (olanzapine coadministered with 10 mg samidorphan using separate tablets) will begin at Visit 6 and last until Visit 8 (randomization). ALKS 3831 treatment will consist of a once-daily dose of olanzapine (with dose level determined by the PI) plus samidorphan 10 mg to be taken at the same time (ie, coadministered) using separate tablets.

At Visit 8, subjects will be randomized in a 1:1 fashion to 1 of 2 treatment groups as follows:

- ALKS 3831 (ie, olanzapine [dose determined by the PI] plus samidorphan [10 mg])
- Olanzapine (dose determined by the PI) plus placebo

Subjects randomized to double-blind treatment will be followed for a minimum of 9 months and a maximum of 15 months. Visits during the double-blind period will be every 2 weeks. Each visit will consist of clinical assessments plus drug dispensing or drug dispensing only. After the end of the double-blind treatment period, subjects will complete a 3-week safety follow-up period.

Figure 1: ALK3831-401 Study Schematic

Abbreviation: V = Study Visit; ALKS 3831=olanzapine + samidorphan

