2. SAMPLE SIZE CONSIDERATION

The sample size calculation is based on the detection of hazard ratio for the first event of exacerbation of disease symptoms (EEDS) during the double-blind treatment period.

Based on the previous clinical studies with olanzapine and clinical judgment, the 9-month cumulative proportion of subjects experiencing an event of exacerbation of disease symptoms (EEDS) will be 15% and 30% for the ALKS 3831 group and olanzapine plus placebo group, respectively. Assuming an exponential distribution of survival time, and a 2-sided test at $\alpha=0.05$, a total of 70 EEDS will be required for approximately 90% power to detect a hazard ratio of 0.45 between ALKS 3831 and olanzapine plus placebo with a randomization allocation ratio of 1:1 (ALKS 3831:olanzapine plus placebo). Approximately 270 subjects (135 subjects per treatment group) will need to be randomized at Visit 8 to observe 70 total EEDS.

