3.8. Safety Analysis

3.8.1. Adverse Events

Adverse events will be coded by System Organ Class and Preferred Term using the Medical Dictionary for Regulatory Activities Version 18.0 (MedDRA®). The verbatim term will be included in the AE listings.

An AE (classified by preferred term) will be considered as treatment-emergent AE (TEAE) if the event is newly occurring or worsening on or after the first dose of study drug.

A TEAE will be summarized for the open-label olanzapine population in the open-label olanzapine period, and for the ALKS 3831 populations in the ALKS 3831 period.

TEAE will be summarized by treatment group for the safety population in the double-blind period. A TEAE will be summarized in the double-blind period if it starts between the date of the

first dose of study drug (inclusive) and the date of the last dose of samidorphan or placebo in the double-blind period.

The number and percentage of subjects reporting TEAEs in each treatment group during the double-blind period will be presented by treatment group and the following categories:

- system organ class and preferred term
- preferred terms in decreasing frequency
- system organ class, preferred term, and severity
- system organ class, preferred term, and relationship
- system organ class, preferred term for drug-related TEAEs

If more than one AE is coded to the same preferred term for the same subject for the same period, the subject will be counted only once for that preferred term using the most severe and most related occurrence for the summarization by severity and by relationship to the study drug.

The incidence of most frequently reported ($\geq 5\%$ of subjects in any treatment group) TEAEs for the double-blind period will be summarized by system organ class, preferred term, and treatment group and will be sorted by decreasing frequency for ALKS 3831 group. It will also be summarized by the olanzapine dose level at randomization.

Newly-emergent AEs (NEAEs), defined as AEs that started or worsened after the date of the last dose of study drug during the treatment period will also be summarized for the follow-up safety population.

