The number and percentage of subjects who have serious adverse events (SAE) will be summarized by preferred term and overall for open-label periods. It will be summarized by preferred term and treatment group for the double-blind period and will be sorted by decreasing frequency for ALKS 3831 group. A listing of subjects with SAEs for entire study will be provided by period. The number and percentage of subjects who have AEs leading to premature discontinuation from the study will be summarized in the same way as SAEs.

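### Double-blind adverse events are summarized only as crude percentages, although time at risk ends when samidorphan/placebo stops and early stopping may differ by arm.

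*SAP*

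**What the plan says.** SAP 3.8.1 sets the measure for TEAEs: "The number and percentage of subjects reporting TEAEs in each treatment group during the double-blind period will be presented by treatment group". For the number and percentage of subjects with SAEs it adds "It will be summarized by preferred term and treatment group for the double-blind period", and "AEs leading to premature discontinuation from the study will be summarized in the same way as SAEs". SAP 3.8.2 gives the SMQ-based events as incidence by arm. Protocol 14.5 takes the same approach: "The incidence of TEAEs will be summarized for each study period, treatment group, and overall by severity and by relationship to study drug", as number and percent of subjects. Neither document plans a person-time rate or a time-to-first-event analysis for any adverse event.

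Two features make time at risk vary.

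- A double-blind TEAE must start between the "first dose of study drug (inclusive) and the date of the last dose of samidorphan or placebo in the double-blind period".
- SAP 1.2 says: "Subjects randomized to double-blind treatment will be followed for a minimum of 9 months and a maximum of 15 months". Subjects who stop early have less.

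Three other provisions bear on the point.

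- SAP 3.6.2 summarizes exposure by arm.
- SAP 3.7.5 compares time to study-drug discontinuation between arms, as an exploratory endpoint.
- SAP 3.7.3.1.2 divides EEDS counts by subject-years and uses a log-time offset. The plan therefore already adjusts for exposure on the efficacy side.

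**The concern.** A crude percentage combines how often an adverse event arises per unit of time with how long subjects were observed. When the two arms have the same exposure this does no harm to the comparison. When they do not, the arm observed longer collects a higher percentage at the same hazard.

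Early stopping could differ here for at least two reasons, and they need not point the same way. EEDS criterion 7 (lack of efficacy, loss to follow-up, withdrawal by the subject) is both a primary-endpoint event and the end of exposure. If ALKS 3831 prevents such events, its subjects stay longer and its crude AE percentages rise. If instead ALKS 3831 loses more subjects for other reasons, such as tolerability, its crude percentages fall and real risk is hidden.

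Safety and tolerability is the trial's only secondary objective, so the AE tables carry that objective.

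**Working it through.** **The plan's own figure.** SAP 2 assumes that the 9-month EEDS proportions "will be 15% and 30% for the ALKS 3831 group and olanzapine plus placebo group, respectively", and that "a total of 70 EEDS will be required for approximately 90% power to detect a hazard ratio of 0.45". With Schoenfeld's formula, power = Φ(√70 × |ln 0.45| / 2 − 1.96) = Φ(1.38) = 91.6%. The hazard ratio implied by the two proportions is ln 0.85 / ln 0.70 = 0.456, which gives 90.8%. The figure reproduces, so the EEDS rates are a fair basis for what follows.

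**Inputs from the documents**

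- EEDS hazards per month under exponential times: −ln(0.85)/9 = 0.0181 for ALKS 3831 and −ln(0.70)/9 = 0.0396 for olanzapine plus placebo.
- 135 subjects per arm.
- Protocol 11.1: a subject with an EEDS other than criterion 7 may continue, at the investigator's discretion.

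**Assumptions not in the documents**

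- Follow-up T is uniform over 9 to 15 months.
- The AE hazard a is 0.03 per month, constant and identical in both arms.
- The stopping hazard d for other reasons is 0.02 per month in both arms, which is 1 − exp(−0.18) = 16% by 9 months.
- A share q of EEDS ends exposure, varied from 0 to 1.

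**Formulas.** The stopping hazard in an arm is h = q × (EEDS hazard) + d. Mean exposure is the average over T of (1 − exp(−hT))/h. The crude AE percentage is the average over T of a/(a+h) × (1 − exp(−(a+h)T)).

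**Results (ALKS 3831 vs olanzapine plus placebo)**

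| Share of EEDS ending exposure | h per month | Mean exposure, months | Crude AE % | Ratio |
|---|---|---|---|---|
| 0 | 0.0200 vs 0.0200 | 10.6 vs 10.6 | 26.9 vs 26.9 | 1.00 |
| 25% | 0.0245 vs 0.0299 | 10.4 vs 10.1 | 26.3 vs 25.5 | 1.03 |
| 50% | 0.0290 vs 0.0398 | 10.1 vs 9.5 | 25.7 vs 24.2 | 1.06 |
| 100% | 0.0381 vs 0.0596 | 9.6 vs 8.5 | 24.5 vs 21.9 | 1.12 |

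The true AE hazards are equal in every row. First events per 100 subject-years at risk would be 0.03 × 12 × 100 = 36.0 in both arms throughout.

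**The reverse direction.** Let other stopping be 4% per month on ALKS 3831 and 2% on olanzapine plus placebo, with a quarter of EEDS ending exposure. The same equal hazard then shows as 23.7% vs 25.5%, which makes ALKS 3831 look safer than it is.

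**A limit of the rate.** Suppose an AE is confined to the first month, with an assumed hazard of 0.2 per month in both arms, every EEDS ending exposure and d = 0.02. Crude percentages are 17.8% vs 17.6%, which is nearly right. Subjects with an event per 100 subject-years are 26.9 vs 29.9, a ratio of 0.90 that falsely favours ALKS 3831. Longer event-free time after the risk period dilutes the rate.

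**The case against.** The strongest reply is that unequal EEDS rates are not unequal exposure. Under Protocol 11.1 a hospitalization, a PANSS worsening, rescue medication or an emergency room visit does not in itself end treatment; only criterion 7 does. The documents assume no discontinuation rate for either arm and give no share of EEDS falling under criterion 7. This stands, and it makes 1.12 an upper bound, not an expectation.

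Nor does the 9 to 15 month range bias the comparison by itself. Scheduled length depends on when a subject was randomized relative to the end of the study, and randomization balances that on average. Only differential early stopping matters. This also stands.

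The distortion is small against sampling error. With 135 per arm, the standard error of the difference in the bottom row is √(0.245 × 0.755/135 + 0.219 × 0.781/135) = 5.1 points, about twice the 2.6-point gap. The AE tables carry no planned test, and a material imbalance would show in the exposure summary, the disposition table and the time-to-discontinuation analysis. All true, but seeing an imbalance does not correct for it. Mean days on drug by arm cannot be turned into first-event time at risk for each AE category.

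For SAEs the equal-hazard premise is doubtful. Hospitalization for worsening is an EEDS under criterion 1, and inpatient hospitalization makes an AE serious. If the drug works, SAE hazards may truly differ, and the shift could favour ALKS 3831.

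Finally, a rate per subject-year is not neutral for early events, as the last calculation shows. Protocol 5.3 says that most samidorphan AEs occur in the first 2 weeks. The 2-week open-label ALKS 3831 period should move most of these before randomization, which weakens the objection without removing it. It is why the rate needs a companion.

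**Conclusion.** The gap in the plan is real and modest. Crude percentages are the only planned AE measure, the TEAE window closes with samidorphan/placebo dosing, and the arms may stop at different rates. Under the planned EEDS rates and the assumptions above, the spurious ratio lies between 1.00 and 1.12. It is about 1.03 to 1.06 if a quarter to a half of EEDS end exposure. Unequal stopping for other reasons can reverse it.

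A reader might infer that the arm expected to have fewer EEDS must look less safe, or that the plan itself predicts longer exposure on ALKS 3831. The documents support neither. Most EEDS permit continued treatment, no difference in discontinuation is assumed, and the net direction cannot be told beforehand. The case for a change rests on the secondary objective, on the low cost, and on the SAP's own use of subject-years for EEDS.

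**What to change.** In SAP 3.8.1 and 3.8.2, keep n (%) and make two additions before unblinding.

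1. For overall TEAEs, TEAEs of at least 5%, SAEs, AEs leading to discontinuation and the SMQ-based events, add subjects with a first event per 100 subject-years at risk, with 95% CI. Count time from the first double-blind dose to the first event or to the end of the AE window.
2. For the main categories, add time-to-first-event cumulative incidence by arm, because the rate assumes a roughly constant hazard and can mislead for front-loaded events. State which estimator is used. Kaplan-Meier with censoring at the last dose describes risk while on drug, and assumes that stopping is unrelated to AE risk. Aalen-Johansen with stopping as a competing event gives the probability of an AE before stopping. It allows for the varying scheduled length but still reflects any difference in stopping between arms.

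Dosing dates are already needed for the exposure summary and AE start dates for the TEAE window, so no new data are required. The cost is a few extra columns and figures, and rates that must be read with the constant-hazard caveat.

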3.8.2. Other significant adverse events

In addition, incidence of selected subset of relevant AEs in this class of drugs, including extrapyramidal symptom (EPS) TEAEs, AEs associated with abuse potential and suicide related events, etc. will be summarized by treatment group and preferred term. The selection of AEs will be based on Standardized MedDRA queries (SMQs).

3.8.3. Clinical Laboratory Parameters

Laboratory parameters will be presented in conventional units. Only scheduled laboratory parameters will be included in the summaries. All laboratory data, including those collected at unscheduled visits, will be included in the listings.

Laboratory results (baseline and change from baseline) for chemistry and hematology parameters will be summarized as overall for open-label periods and by treatment group for the double-blind period.

Clinical laboratory test values, scheduled or unscheduled, will be considered potentially clinically significant (PCS) if they meet PCS criteria listed in Table 2. The number and percentage of subjects who have PCS post baseline clinical laboratory values will be tabulated by treatment group for the double-blind period. The percentages will be calculated relative to the number of subjects with available non-PCS baseline values and at least 1 post baseline assessment for the double-blind treatment period. The numerator will be the total number of subjects with available non-PCS baseline values and at least 1 PCS post baseline value for the double-blind treatment period. A supportive tabular display of subjects with PCS post baseline values will be provided, including the subject ID number, study center number, baseline, and all post baseline (including non-PCS) values.

Table 2: Criteria of Potentially Clinically Significant (PCS) Abnormality for Selected Analytes

Parameters	Criteria
Albumin	<2.5 g/dL
Alkaline phosphatase (U/L)	$\geq 3 \times \text{ULN}$
Alanine aminotransferase (U/L)	$\geq 3 \times \text{ULN}$
Aspartate aminotransferase (U/L)	$\geq 3 \times \text{ULN}$
Bilirubin, total	$\geq 2.0 \text{ mg/dL}$
Blood urea nitrogen	$> 30 \text{ mg/dL}$
Cholesterol, random	$> 300 \text{ mg/dL}$
Cholesterol, fasting	$\geq 240 \text{ mg/dL}$
Cholesterol, HDL fasting	$\leq 30 \text{ mg/dL}$
Cholesterol, LDL fasting	$\geq 160 \text{ mg/dL}$
Creatine kinase (U/L)	$\geq 3 \times \text{ULN}$
Creatinine	$\geq 2.0 \text{ mg/dL}$
Glucose, random	$< 50 \text{ mg/dL}$ or $\geq 200 \text{ mg/dL}$
Glucose, fasting	$\geq 126 \text{ mg/dL}$
Potassium	$< 3 \text{ mmol/L}$ or $> 5.5 \text{ mmol/L}$
Lactate dehydrogenase (U/L)	$> 3 \times \text{ULN}$
Phosphate	$< 2 \text{ mg/dl}$ or $> 5 \text{ mg/dl}$
Prolactin (female)	$> 30 \text{ ng/mL}$
Prolactin (male)	$> 20 \text{ ng/mL}$
Sodium	$< 130 \text{ mmol/L}$ or $> 150 \text{ mmol/L}$

Table 2: Criteria of Potentially Clinically Significant (PCS) Abnormality for Selected Analytes (Continued)

Parameters	Criteria
Triglycerides, fasting (female)	≥ 120 mg/dL
Triglycerides, fasting (male)	≥ 160 mg/dL

Table 3: Potentially Clinically Significant Results Criteria for Hematology

Parameters	Criteria
Eosinophils	$> 1.0 \times 10^3/\mu\text{L}$
Hematocrit (female)	$\leq 32\%$
Hematocrit (male)	$\leq 37\%$
Neutrophils, absolute	$< 1.5 \times 10^3/\mu\text{L}$
Platelets	$< 75.0 \times 10^3$ cells/ μL or $\geq 700.0 \times 10^3$ cells/ μL
Leukocytes	$\leq 2.8 \times 10^3/\mu\text{L}$ or $\geq 16.0 \times 10^3/\mu\text{L}$

Shift tables for metabolic parameters (glucose, total cholesterol, LDL, HDL, triglycerides, and HbA1c) will be presented.

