16. Has unstable thyroid dysfunction within the 6 months prior to screening (eg, hypothyroidism, hyperthyroidism, or thyroiditis that was untreated or was discovered and resulted in treatment within the 6 months prior to screening) or a thyroid stimulating hormone (TSH) level higher than 10% above the upper limit of the normal range at screening.
17. Has a neurologic condition, including (but not limited to) the following:
 - History of seizure disorder or a condition associated with seizures (excluding febrile seizures but including seizures associated with substance use or withdrawal) within the past 6 months
 - History of brain tumor, subdural hematoma, or other clinically significant neurological condition within the 1 year prior to screening
 - Head trauma with a loss of consciousness within 30 days prior to screening

- An active acute or chronic central nervous system infection
 - History of stroke or cerebrovascular infarction
18. Has dyslipidemia (total cholesterol >280 mg/dL or triglycerides >500 mg/dL at screening)
19. Has diabetes or meets any of the following criteria at screening:
- Hemoglobin A1c (HbA_{1c}) ≥6.5%
 - A random plasma glucose ≥200 mg/dL (11.1 mmol/L)
20. Has a laboratory abnormality at screening, including (but not limited to) the following (clinical laboratory assessments may be repeated if the PI feels the test may be in error):
- Aspartate aminotransferase or alanine aminotransferase value ≥3 times the upper limit of the laboratory normal reference range
 - Absolute neutrophil count ≤1.5 × 10³ per μL
 - Platelet count ≤75 × 10³ per μL
 - Serum creatinine >2.5 mg/dL
21. Has no living arrangements available at screening or Visit 2, consistently lacks or loses housing (such that maintaining contact with the subject will be difficult), or has plans to leave the study site area during the study period
- A temporary loss of living arrangements due to loss of caregiver support or other circumstances (eg, recent symptom exacerbation) is allowed if housing is typically available when schizophrenia and AUD symptoms are stable and not exacerbated.

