8.3.22. Hematology, Biochemistry, and Urinalysis

Blood and urine samples for laboratory assessments will be collected at the time points specified in [Table 1](#), [Table 2](#), and [Table 3](#). Specific hematology, biochemistry, and urinalysis assessments are listed in [Table 4](#). Samples will be collected in accordance with the site’s usual procedures

and analyzed by a central laboratory. Follow-up samples may be obtained for repeat testing as clinically indicated.

An absolute neutrophil count $\leq 1.0 \times 10^3$ per μL anytime while on olanzapine should be cause for discontinuing a subject. A second test can be performed within 24 hours of availability of the laboratory result to confirm the finding if the investigator feels the result may be in error. Otherwise, the subject should be discontinued.

For all timepoints (except screening) where samples will be collected, fasting assessments (fasting for at least 10 hours prior to collecting samples) should be attempted as per standard of care [[Lilly USA 2013](#)]. However, fasting may present challenges, including an increased frequency of missed visits and re-scheduling, that could negatively impact the subject's treatment. Therefore, failure to fast should not be considered a protocol deviation.

Whether or not a subject fasts and the number of hours since the subject's last meal will be entered onto the appropriate eCRF.

TSH will only be measured at screening.

Table 4: Clinical Laboratory Assessments

Hematology	Biochemistry	Urinalysis

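### SAP Table 2 gives fasting glucose no lower PCS limit, and non-fasting triglycerides no limit at all; add the first and explain or fill the second (minor)

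*SAP*

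**What the plan says.** The rule in SAP 3.8.3 is "Clinical laboratory test values, scheduled or unscheduled, will be considered potentially clinically significant (PCS) if they meet PCS criteria listed in Table 2". The output is a subject count: "The number and percentage of subjects who have PCS post baseline clinical laboratory values will be tabulated by treatment group for the double-blind period". The denominator is subjects whose baseline is on record and not PCS and who have a later value; the numerator is those among them with at least one PCS value after baseline. Protocol 14.5 leaves all PCS limits to the SAP, so there is no fallback elsewhere.

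The glucose and lipid rows of Table 2 are:

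| Analyte | Random | Fasting |
|---|---|---|
| Glucose | <50 or ≥200 mg/dL | ≥126 mg/dL |
| Total cholesterol | >300 mg/dL | ≥240 mg/dL |
| HDL | no row | ≤30 mg/dL |
| LDL | no row | ≥160 mg/dL |
| Triglycerides, women | no row | ≥120 mg/dL |
| Triglycerides, men | no row | ≥160 mg/dL |

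The SAP does not define random.

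Protocol 8.3.22 asks sites to attempt fasting whenever samples are taken, except at screening. It accepts that this will sometimes not succeed: "failure to fast should not be considered a protocol deviation". Fasting status and hours since the last meal go on the eCRF, so each value can be classed.

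**The concern.** The two glucose rows do not cover the same directions. "Glucose, random" has a lower and an upper limit; "Glucose, fasting" has only an upper one. Fasting is the intended state at every draw after screening, so on the natural reading the low limit applies only where the intended condition was not met. Whether a low value is counted then depends on whether the subject had eaten, not on how low it was.

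Triglycerides raise a related question. The only rows are those beginning "Triglycerides, fasting (female" and "Triglycerides, fasting (male", so a non-fasting sample, which the protocol accepts, cannot be PCS at any level.

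The tables concerned are descriptive, but they bear on the study's secondary objective of safety and tolerability. The protocol's introduction itself names metabolic effects as a limit on olanzapine use.

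**Working it through.** The plan states no figure to reproduce. The check is to run test values through the Table 2 rows under both possible meanings of random.

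| Test value | Random = non-fasting | Random = any sample |
|---|---|---|
| Fasting glucose 30 mg/dL | not PCS | PCS |
| Fasting glucose 49 mg/dL | not PCS | PCS |
| Non-fasting glucose 49 mg/dL | PCS | PCS |
| Fasting glucose 126 mg/dL | PCS | PCS |
| Non-fasting triglycerides 501 mg/dL, man | not PCS | not PCS |
| Non-fasting triglycerides 1500 mg/dL, man or woman | not PCS | not PCS |
| Fasting triglycerides 160 mg/dL, man | PCS | PCS |
| Non-fasting LDL 250 or HDL 20 mg/dL | not PCS | not PCS |

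A fasting glucose of 40 mg/dL behaves like the 30 and 49 rows.

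**Which reading is natural.** Glucose and total cholesterol each have two rows, and the upper limit is higher in the random row (200 against 126; 300 against 240). If random meant any sample, the random upper limit would add nothing for a fasting sample, since a fasting glucose of 200 already exceeds 126. The pairing makes sense as non-fasting against fasting. On that reading the fasting-glucose gap is real. The triglyceride result is the same on either reading.

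**Baseline.** A non-fasting triglyceride baseline meets no criterion, so it always counts as non-PCS. A man with 900 mg/dL non-fasting at Visit 8 and 160 mg/dL fasting later would enter the denominator as non-PCS and then count as a case. The miscount can therefore run in either direction.

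**Size.** The documents do not give the share of non-fasting samples, f, or the frequency of extreme values, so no count can be computed. What can be shown is the effect of repeated draws. Protocol Table 2 schedules post-baseline laboratory tests at Visits 10, 14, 20 and 26, which is four, and Protocol Table 3 adds more for longer follow-up. Suppose a subject with very high triglycerides exceeds the fasting limit whenever fasting, completes four draws and fasts independently at each. The subject is missed only if all four are non-fasting, with probability f⁴. For an assumed f of 0.2 to 0.6:

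- 0.2⁴ = 0.0016
- 0.6⁴ = 0.1296

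That is about 0.2% to 13%. Dropout, or subjects who habitually do not fast, would raise it.

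For low glucose, repeated draws help less: a subject with one low fasting value is picked up only if a non-fasting value is also below 50 mg/dL. Against that, Protocol 7.2 excludes subjects with diabetes and those on hypoglycemic agents, so few such values would be expected; that is a judgment, not a figure from the documents.

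**The case against.** **The word random is undefined.** If it means a sample at any time, the <50 mg/dL limit already covers fasting samples and the glucose gap closes. This stands as a limit on the point. It does not count against the edit, which would then only make explicit what was meant.

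**The lipid omission may be a choice.** Table 2 covers selected analytes, and HDL, LDL and triglycerides are all fasting-only. Three fractions treated alike could well be deliberate. This stands, and it is why the triglyceride part is a request to decide and say so, not a claim of error.

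**The values appear elsewhere.** By-arm chemistry summaries include the minimum and maximum, glucose and triglycerides have shift tables, everything is listed, and values that the investigator judges clinically significant become adverse events. A reader might infer that extreme values would vanish from the report; they would not. But none of these outputs replaces the subject count. A range does not count subjects, and by-visit summaries leave out unscheduled values, which the PCS table includes. The shift tables have no stated categories or fasting rule, and adverse event capture rests on site judgment.

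**Both arms follow the same rule.** No hypothesis test is affected, and nothing in the documents suggests that fasting will differ by arm. This stands and keeps the severity low.

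**Conclusion.** The point holds as a minor one. On the natural reading of Table 2, low fasting glucose is left out of the by-arm PCS count while a less extreme non-fasting value is included. This rests on random meaning non-fasting. The triglyceride observation does not depend on that reading, but it may reflect a decision that the SAP does not state.

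Two stronger inferences are tempting and not supported:

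- A reader might multiply an assumed number of affected subjects by an assumed share of non-fasting samples, and conclude that several subjects per arm would go uncounted. With 3–5% of 135 subjects (4.05 to 6.75) and f of 0.2 to 0.6, that gives about 1 to 4. Both inputs are assumptions, and the step applies a per-sample share to a table that counts a subject on any one PCS value over at least four scheduled draws by Visit 26. The true number is unknown and probably small.
- A reader might take the screening criterion, "Has dyslipidemia (total cholesterol >280 mg/dL or triglycerides >500 mg/dL at screening", as settling the non-fasting PCS limit. It is an eligibility limit. The same criterion uses 280 mg/dL for total cholesterol, while the SAP's random PCS limit is >300 mg/dL, so the SAP did not simply carry screening limits over.

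**What to change.** 1. In SAP Table 2, change the fasting-glucose criterion to <50 mg/dL or ≥126 mg/dL. The lower figure is the one that the table already uses for random glucose. It is a reporting limit and touches no patient care. The only downside is possibly a slightly higher PCS count.
2. Define random in SAP 3.8.3, by reference to the fasting status on the eCRF.
3. For triglycerides, either set a non-fasting limit, for which the protocol's >500 mg/dL at screening is one candidate, or state that non-fasting lipid fractions (triglycerides, HDL and LDL) are deliberately outside the PCS table.
4. If a non-fasting triglyceride row is added, state which baseline sample applies. The percentage requires a non-PCS baseline, and if a fasting Visit 8 sample could not serve for that row, many subjects might drop out of its denominator.

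Items 1 and 2 are short text edits. Items 3 and 4 need a decision before database lock and some programming, but no new data.
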